9.7 Visit 10 (Day 140 ± 5): Week 20/End of Study

At this visit, the investigator or designee will:

- Query the subject for any changes in health status since the previous visit, including concomitant medications and concurrent procedures/therapies, and document the findings.
- Perform a physical examination ([Section 10.4.1](#)).
- Measure vital signs ([Section 10.4.2](#)) if any new or worsening clinically significant abnormalities were present at EOT, or as warranted based on the subject's current medical condition.
- Perform 12-lead ECG ([Section 10.4.3](#)) if any new or worsening clinically significant abnormalities were present at EOT, or as warranted based on the subject's current medical condition.
- Collect urine and blood samples for clinical labs (chemistry [including lipid panel and thyroid function], hematology, urinalysis, and cardiac biomarkers; [Section 12.1](#)) if any new or worsening clinically significant abnormalities were present at EOT, or as warranted based on the subject's current medical condition. Note: It is preferred that subjects be fasting (approximately 8 hours); however, if a subject arrives at the clinic without fasting for at least 8 hours, laboratory specimens may be collected as non-fasting, at the discretion of the investigator, and with the appropriate fasting status documented on the lab requisition form.
- Record LSRs ([Section 10.4.4](#)).
- Document any AEs.
- Exit subject from the study.

[figure not shown]
10. CLINICAL EVALUATIONS

The following clinical evaluations will be performed according to the Schedule of Events (SOE). The same expert grader who has received training on how to properly perform the clinical evaluations should ideally complete the evaluations for a given subject throughout the study. If this is not possible (e.g., scheduling conflict), a different expert grader with overlapping experience with the subject and the study should complete the evaluations.

10.1 Modified Norwood-Hamilton Scale

The Modified Norwood-Hamilton Scale will be used at Visit 1/Screening to classify the pattern of hair loss and determine subject eligibility. Subjects must have mild to moderate AGA in the temple and vertex region, rating IIIv to V on the Modified Norwood-Hamilton Scale (i.e., IIIv, IV, and V), to be eligible for the study. The Modified Norwood-Hamilton Scale describes the most regular patterns for male pattern baldness [[15](#)].

Figure 10.1-1 Modified Norwood-Hamilton Scale Describing Male Pattern Baldness

- **Type I.** No recession or very minimal recession along the anterior border of the hairline in the frontotemporal region.
- **Type II.** The anterior border of the hair in the frontotemporal region has triangular areas of recession which tend to be symmetrical. These areas of denudation extend no further posteriorly than approximately 2 cm anterior to a line drawn in a coronal plane between the external auditory meatus. Hair also is lost, or sparse, along the midfrontal border of the scalp, but the depth of the affected area is much less than in the frontotemporal region.
- **Type III.** This represents the minimal extent of hair loss considered sufficient to represent baldness. Most type III scalps have deep frontotemporal recessions which are usually symmetrical and are either bare or very sparsely covered by hair. These recessions extend further posteriorly than a point which lies approximately 3 cm anterior to a coronal line drawn between the external auditory meatus.
- **Type IV.** The frontal and frontotemporal recession is more severe than in type III. Also, there is sparseness or absence of hair on the vertex area. These areas are extensive but separated from each other by a band of moderately dense hair that extends across the top. This band joins the fully haired fringe on each side of the head.
- **Type V.** The vertex region remains separated from the frontotemporal region. The separation is now not as distinct, because the band of hair across the crown has become narrower and sparser. Both the vertex and frontotemporal areas of hair loss have become larger.
- **Type VI.** The bridge of hair that crossed the crown in the previous type is now gone. The frontotemporal and vertex regions of hair loss have become confluent, and in addition the entire area of hair loss has increased laterally and posteriorly.
- **Type VII.** This is the most severe form of male pattern baldness. All that remains is a narrow horseshoe-shaped band of hair which begins laterally just anterior to the ear and extends posteriorly on the sides and quite low on the occiput. This hair is usually not dense and frequently is fine. The hair is also extremely sparse on the nape of the neck and in a

semicircle over both ears. It should be noted that the anterior border of this band on each side of the head has receded posteriorly to just in front of the ears.

10.2 Investigator's Global Assessment

The evaluator will use standardized global photos (i.e., a vertex view and a superior view) of the subject's scalp taken at Visit 1/Screening and will compare them to the current visit's photos of the subject's scalp hair growth using the Canfield Review application. The evaluator will assess the subject's scalp hair growth using the following 7-point scale: greatly decreased (-3), moderately decreased (-2), slightly decreased (-1), no change (0), slightly increased (1), moderately increased (2), and greatly increased (3).

10.3 Subject Self-Assessment

The subject will use the standardized global photos (i.e., a vertex view and a superior view) of the subject's scalp taken at Visit 1/Screening and will compare them to the current visit's photos of subject's scalp hair growth for HGA and HGI which comprise the SSA.

10.3.1 Hair Growth Assessment

Scalp hair growth will be compared from Baseline using the following 7-point scale: greatly decreased (-3), moderately decreased (-2), slightly decreased (-1), no change (0), slightly increased (1), moderately increased (2), and greatly increased (3).

10.3.2 Hair Growth Index

Scalp hair growth will be compared from Baseline using the following 7-point scale: much less (-3), moderately less (-2), slightly less (-1), the same amount (0), slightly more (1), moderately more (2), and much more (3) for the following 3 questions:

1. "Since the start of treatment, when I look at my thinning area, I can see ... (scalp)";
2. "Since the start of treatment, my hair now covers ... (scalp)"; and
3. "Since the start of treatment, the appearance (thickness/quality/ amount) of the thinning area on my head is ..."

10.4 Safety Evaluations

10.4.1 Physical Examination

Physical examinations will be performed per the SOE. Assessments will include examination of head and neck, dermatologic (except the indication being studied), cardiovascular, respiratory, gastrointestinal (abdomen), and gross motor and gait. Clinically significant abnormalities at Visit 1/Screening and Visit 2/Baseline will be recorded as medical history. Any new or worsening clinically significant abnormalities after first dose of IP will be recorded as AEs.

10.4.2 Vital Signs

Vital signs including temperature, systolic and diastolic blood pressure, heart rate, and respiration rate will be measured per the SOE. Assessments will be made after the subject has rested in a seated position for at least 5 minutes. Height, weight, and BMI will also be measured at Visit 1/Screening and Visit 9/EOT.

10.4.3 Electrocardiogram

ECGs will be performed per the SOE. 12-lead ECGs will be performed after the subject has rested for at least 10 minutes in the supine position. ECG results will be recorded on the appropriate eCRF.

The Investigator must review all the ECG reports in a timely manner. Note: The Investigator will initial and date each ECG report to indicate his/her review. The Investigator will note, directly on the report, whether or not any abnormal findings are clinically significant. The Investigator must complete an appropriate AE form for any new or worsening abnormal test results that are identified as clinically significant after Baseline.

10.4.4 Local Skin Reactions

LSRs will be collected per the SOE. LSRs of erythema, edema, erosion, scaling, pruritus, and burning/stinging will be assessed using a 5-point ordinal scale (0=none, 1=minimal, 2=mild, 3=moderate, and 4=severe). Only reactions that require medical intervention (e.g., prescription medication) will be documented as AEs. Any reactions to the IP that are not listed above will be recorded as AEs.

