14.1 Adverse Event Definitions

An **adverse event** is any untoward medical occurrence associated with the use of a drug in humans, whether or not considered related.

An AE (also referred to as an adverse experience) can be any unfavorable and unintended sign (e.g., an abnormal laboratory finding), symptom, or disease temporally associated with the use of a drug, without any judgment about causality. An AE can arise from any use of the drug (e.g., off-label use, use in combination with any drug) and from any route of administration, formulation, or dose, including an overdose.

A **suspected adverse reaction** is any AE for which there is a reasonable possibility that the drug caused the event. "Reasonable possibility" means there is evidence to suggest a causal relationship between the drug and the AE.

An **adverse reaction** is any AE caused by a drug. Adverse reactions are a subset of all suspected adverse reactions for which there is reason to conclude that the drug caused the event. A suspected adverse reaction implies a lesser degree of certainty about causality than adverse reaction, which means any AE caused by a drug. For the purposes of prescription drug labeling, the term adverse reaction means an undesirable effect, reasonably associated with the use of a drug that may occur as part of its pharmacological action or may be unpredictable in its occurrence.

An AE or suspected adverse reaction is considered "unexpected" if it is not listed in the IB or is not listed at the specificity or severity that has been observed. For example, under this definition, hepatic necrosis would be unexpected (by virtue of greater severity) if the IB referred only to elevated hepatic enzymes or hepatitis. Similarly, cerebral thromboembolism and cerebral vasculitis would be unexpected (by virtue of greater specificity) if the IB listed only cerebral

vascular accidents. "Unexpected," as used in this definition, also refers to AEs or suspected adverse reactions that are mentioned in the IB as occurring with a class of drugs or as anticipated from the pharmacological properties of the drug, but are not specifically mentioned as occurring with the particular drug under investigation.

Timely and complete reporting of all AEs assists the Sponsor and/or their designee (e.g., Therapeutics, Inc. [TI]) in identifying any untoward medical occurrence, thereby allowing:

- 1) protection of the safety of study subjects;

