14.2 Adverse Event Details

AEs may be either spontaneously reported or elicited during questioning and examination of a subject. All AEs must be recorded on the AE eCRF. If known, the investigator should report the diagnosis of the underlying illness or disorder, rather than its individual symptoms. Subjects experiencing AEs that cause interruption or discontinuation of IP or those experiencing AEs that are present at the end of their participation in the study should receive follow-up as appropriate. AEs should be followed to resolution or stabilization (if possible) and, if they become serious, reported as serious adverse events (SAEs, see [Section 14.3](#)). If possible, the outcome of any AEs that caused permanent discontinuation or that were present at the end of the study, especially those considered by the investigator to be related to the IP, should be reported.

Information on the medical condition of subjects should begin following the subject's written informed consent to participate in the study and a medical history should be taken at screening. During any wash out and screening periods, any changes in the health of subjects should be recorded as changes in medical history unless an event occurred as a result of a study-related procedure and is unanticipated; in such cases, the event should be recorded as an AE and reported to the Institutional Review Board (IRB) as an "unanticipated problem" in accordance with local procedures. Other changes in subject health information becomes AE data when the subject begins dosing with the IP; therefore AE data should be collected from the date of the first dose of IP until the date of the final study visit. These data are considered treatment-emergent AEs.

The investigator will instruct the subject to report any AEs that may occur during the study. At each visit, the investigator should ask the subject, in non-directive fashion, about any change in the subject's overall health status since the previous visit.

The severity of each AE, as judged by the investigator, will be recorded on the appropriate AE eCRF and will be graded according to the following scale:

Mild: The AE is usually transient and may require only minimal treatment or therapeutic intervention. The event does not generally interfere with usual activities of daily living.

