17.3.2 Safety Endpoints

1. Incidence (severity and causality) of any local and systemic AEs.
2. Number of subjects with presence (and severity) of the following LSRs: erythema, edema, erosion, scaling, pruritus, and burning/stinging at each time point.
3. Changes from Baseline in vital signs at each time point.
4. Changes from Baseline in clinical laboratory tests (chemistry [including lipid panel and thyroid function], hematology, and urinalysis, and cardiac biomarkers) at Week 4, Week 8, Week 12, and Week 16.
5. Changes from Baseline in ECG parameters and overall ECG interpretation at Week 4, Week 8, Week 12, and Week 16.

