At each post-Baseline visit, site staff will collect all droppers (used and unused) of the IP and record the necessary information in the IP Accountability Log. Site staff will review the IP application procedure and subjects will be counseled on IP compliance, as necessary. Any

discrepancies or concerns with the subject regarding the use of the Subject Diary to record IP applications should be addressed. At the end of subject's participation in the treatment phase, the total group of returned unit dose droppers will be weighed.

A 3.4 Investigational Product Supply Records at Study Sites

It is the responsibility of the investigator to ensure that a current record of IP disposition is maintained. Records or logs must comply with applicable regulations and guidelines, and should include:

- Amount received placed in storage area.
- Amount currently in storage area.
- Label ID number or batch number.
- Dates and initials of the person responsible for each product inventory entry/movement.
- Amount (number and units and weights) dispensed to and returned by each subject, including unique subject identifiers.
- Amount transferred to another area for dispensing or storage.
- Non-study disposition (e.g., lost, wasted, broken).
- Amount returned to Sponsor.
- Amount destroyed at study site, if applicable.

TI will provide forms to facilitate inventory control if the staff at the study site does not have an established system that meets these requirements.

A 3.5 Dose Modifications

The subject should not modify the treatment regimen without consultation with the Investigator. Subjects should be instructed to discontinue use if skin irritation or rash develops and to contact the study site immediately. In the event that the Investigator believes that dose modification is necessary (e.g., problems with tolerance), the subject's care should be discussed with the Medical Monitor prior to making any dose modifications. All dose modifications must be reported on the appropriate eCRF.

A 3.6 Documentation of Application and Compliance

The date of the first and last application of the IP will be recorded on the appropriate eCRF. Dosing times relative to PK blood draws will also be collected in the appropriate eCRF. An eCRF will also be used to record any changes from the application specified in the protocol (e.g., investigator directed reduction in application frequency or drug holiday).

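### A listed local skin reaction that makes a subject interrupt, reduce or stop IP without medical intervention gets no AE record on the literal text, and no planned output links local reactions to changes in IP use

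*Protocol*

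**What the plan says.** Protocol 10.4.4 grades erythema, edema, erosion, scaling, pruritus and burning/stinging from 0 to 4. On when these become AEs it says: "Only reactions that require medical intervention (e.g., prescription medication) will be documented as AEs". The synopsis and SAP 7.4 carry the same rule. Reactions outside the list are treated differently: "Any reactions to the IP that are not listed above will be recorded as AEs".

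The surrounding text is broader:

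- Protocol 14.1 says that an AE "can be any unfavorable and unintended sign (e.g., an abnormal laboratory finding), symptom, or disease temporally associated with the use of a drug".
- Protocol 14.2 requires every AE to go on the AE eCRF with severity, relationship to IP and outcome, and asks for follow-up of "Subjects experiencing AEs that cause interruption or discontinuation of IP".
- Safety endpoint 1 (Protocol 17.3.2, SAP 3.3) is, in the protocol's words, "Incidence (severity and causality) of any local and systemic AEs". Safety endpoint 2 is the presence and severity of each LSR at each time point.

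Appendix 3, A 3.5 foresees treatment changes for local intolerance: "Subjects should be instructed to discontinue use if skin irritation or rash develops and to contact the study site immediately". It also allows for investigator-directed dose changes when tolerance is a problem, and adds: "All dose modifications must be reported on the appropriate eCRF".

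**The concern.** Medical intervention is the only stated route by which a listed LSR becomes an AE, and a change in IP use is not a trigger. A subject with grade 4 burning who stops applying the product and receives no treatment therefore falls outside the AE definition as written, while a trivial unlisted reaction falls inside it.

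Tolerability is part of the second study objective, and the two active strengths differ eightfold (0.0025% and 0.02%). For a topical product, reactions that alter treatment are among the most useful to compare between arms. If they go unrecorded as AEs, the local part of safety endpoint 1 is incomplete, and they have no causality assessment or outcome. The LSR gradings carry neither.

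**Working it through.** The documents give no figure on this point to reproduce. The check sets the planned outputs side by side, followed by two pieces of arithmetic for scale.

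**1. Does any planned output link an LSR to a change in IP use?**

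| Output | What it shows | Link to IP change |
|---|---|---|
| LSR table (Protocol 17.4.2.6, SAP 8.9.3) | Frequency and severity of each LSR by arm | None |
| AE tables (SAP 8.9.6) | SOC, PT, severity, relationship; serious AEs | No table of AEs leading to interruption, modification or discontinuation |
| Disposition (SAP 8.6) | Reasons for leaving the study | Does not cover interruption or reduction while staying in the study |
| Exposure (SAP 8.9.1) | Last minus first application date plus 1; amount used | An interruption does not shorten the duration; no reasons given |
| Compliance (SAP 8.8.1.3) | Number of applications | No reasons given |
| Dose-modification eCRF (A 3.5, A 3.6) | Data collected | No SAP summary planned |

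None of these outputs makes the link.

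**2. Effect of one subject on AE incidence.** The planned arm size is 24 (synopsis). One subject who is not counted and has no other AE changes the arm's incidence by 1/24 = 4.2 percentage points, or 1/48 = 2.1 points across both active arms together.

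**3. Can the visit grading miss such a reaction? (illustration only)**

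- Inputs from the Schedule of Events: LSRs are graded at Baseline and Weeks 2, 4, 8, 12, 16 and 20, and not at the two phone contacts. In whole weeks the on-treatment gaps are 14, 14, 28, 28 and 28 days, which total 112.
- Assumptions that are not in the documents: onset is uniform over the 112 days; grading covers only the visit day; visits fall on schedule with no extra visit; and the reaction lasts 3, 7 or 14 days.
- Formula: a reaction lasting d days falls wholly inside a gap of length g if it starts in the first g − d days. The share missed is therefore the sum of (g − d) over the gaps, divided by 112.

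| d (days) | Sum of (g − d) | Share between gradings |
|---|---|---|
| 3 | 11 + 11 + 25 + 25 + 25 = 97 | 97/112 = 87% |
| 7 | 7 + 7 + 21 + 21 + 21 = 77 | 77/112 = 69% |
| 14 | 0 + 0 + 14 + 14 + 14 = 42 | 42/112 = 37.5% |

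These shares describe any short reaction under those assumptions.

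**4. Passages that disagree on stopping.** A 3.5 has subjects discontinue when irritation or rash develops. The Subject Instruction Sheet (Appendix 1, application step 9) has them continue unless the study doctor directs otherwise and contact staff before stopping. How often IP is stopped for an LSR depends on which text a site follows.

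**The case against.** Keeping graded LSRs apart from AEs is a reasonable way to avoid double counting, and LSRs have their own endpoint and table. Much of the information on subjects who stop is also collected. Visit 9 doubles as the early termination visit and includes LSR grading. Section 13.2 asks sites to make every effort to bring withdrawing subjects back. Withdrawal reasons are tabulated by arm, and subjects are told to contact the site immediately about irritation. The rule is the same in every arm under blinding, and Protocol section 2 reports these strengths as well tolerated in the earlier studies. Medical intervention is also undefined, and prescription medication is only an example, so an investigator could count a directed dose change as intervention. All of this stands, and it limits the point to AE recording and the missing link. The undefined term does not remove the problem, because sites could then record the same event differently.

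Four stronger readings are tempting, and the documents do not support them:

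- **Treatment-limiting irritation disappears from the results.** It does not if it is present at a graded visit.
- **A stop for an LSR cannot be coded as due to an AE.** Section 13.2 offers AEs as a withdrawal reason and states no need for a matching AE record. The fault is an inconsistency: a withdrawal could be coded to an AE that has no record.
- **69% is the chance of losing a treatment-limiting reaction.** That figure rests on assumed durations and onset, covers mild reactions too, and ignores early termination visits and the instruction to contact the site.
- **The rule is what removes the action taken with IP.** For AEs generally the protocol specifies severity, relationship and outcome. Action taken is mentioned only for laboratory abnormalities (14.4), so an AE record alone would not supply it.

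**Conclusion.** The point holds as a gap in recording and reporting. On the literal text, a listed LSR that changes IP use without medical intervention gets no AE record and is not counted in safety endpoint 1, although A 3.5 foresees that situation and the definitions in 14.1 and 14.2 would otherwise cover it. The LSR, disposition and dose-modification data preserve part of the information, but nothing planned joins them.

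The size is 4.2 percentage points of arm-level AE incidence per affected subject, assuming 24 per arm and no other AE in that subject. The number of affected subjects is unknown. The between-visit shares show only that LSR grading is not a complete backstop. This is a cheap improvement worth making, and it does not show that the safety comparison is invalid.

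**What to change.** 1. In Protocol 10.4.4, the synopsis and SAP 7.4, state that listed LSRs are documented as AEs if they require medical intervention or lead to interruption, modification or discontinuation of IP. This also settles how an investigator-directed change is recorded, whatever medical intervention is taken to mean.
2. In SAP 8.9.6, add a by-arm table of AEs leading to interruption, modification or discontinuation of IP, built with the dose-modification eCRF. The eCRF is not among the documents, so confirm that it records the reason for each change. A table of worst post-baseline LSR grade would not do this job, because it uses the same visit gradings and recovers no between-visit reaction.
3. Reconcile A 3.5 with step 9 of the Subject Instruction Sheet on stopping for irritation. Which text is right is for the sponsor to settle.

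Items 1 and 2 change recording and reporting, not clinical management. The cost is one clause in three places, one table, a few more AE records and a slightly less favourable local-AE count.
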